#### **4.4 Study Duration**

Expected enrollment duration is 12 months, patients will remain on study treatment until PSA progression defined by PCWG3 (unless they meet the criteria for continued treatment outlined in section 6.4.1), with 2 years of follow up after study treatment. We anticipate a total of 2-3 years until completion of the clinical trial.

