8. If treatment is discontinued prior to PSA progression, PSA testing will continue throughout follow-up until PSA progression or start of another treatment. Patients who have PSA progression prior to discontinuing treatment do not need to have PSA testing performed during follow-up.
9. Rucaparib will be administered as described in Section 6.
10. Blood collection for biomarkers will be collected at screening, C3D1, C7D1, and confirmed PSA disease progression ( $\pm 7$  days), if applicable, or at EOT visit (whichever occurs first).

11. For patients enrolled with an intact prostate, urine collection for biomarkers will be collected at screening, C3D1, C7D1, and confirmed PSA disease progression ( $\pm$  7 days), if applicable, or at EOT visit (whichever occurs first).
12. Archival tissue will be collected at screening (if available). Archival tissue should not be cut until instructed by the central lab.
13. Genomic or genetic testing for 'BRCAness' will be confirmed with either blood or tissue based testing.
14. An optional fresh tissue biopsy may be obtained at PSA Progression Confirmation Visit ( $\pm$  28 days) for subjects with radiographic disease progression.
15. CT scans of the chest/abdomen and pelvis and NM bone scans will be done at the time of PSA Progression Confirmation Visit ( $\pm$  28 days) as defined in section 10.1.
16. Follow-up should occur every 90 days ( $\pm$  14 days) for 2 years following End of Treatment as per standard of care (section 9).
17. Coagulation Panel includes PT/INR, PTT.
18. The end of treatment visit should occur within +/-3 days of the decision to discontinue treatment. If this visit overlaps with a regularly scheduled visit, only the procedures listed in the calendar for the EOT visit will be performed.
19. To be performed only if the subject has completed hormone therapy. Screening testosterone may be performed within 84 days of study enrollment.
20. Only patients who have suspected PSA progression during a regular study visit will have testing to confirm PSA progression at their next regularly scheduled visit. **Before continuation of treatment after confirmed PSA progression, the patient must agree to sign the Treatment After Progression Informed Consent Form.** Patients may complete the assessments required for PSA progression in conjunction with the next regularly scheduled cycle visit or at EOT.

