## **9.5 Follow-up Evaluations Q 90 days ( $\pm$ 14 days)**

Survival follow-up, including survival status and post-study treatments. Follow-up may be conducted via phone call or record review if laboratory assessments are not required.

- Laboratory assessments:
  - If treatment is discontinued prior to PSA progression, PSA testing will continue throughout follow-up until PSA progression or start of another treatment. Patients who have PSA progression prior to discontinuing treatment do not need to have PSA testing performed during follow-up.

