# **10 CRITERIA FOR EVALUATION AND ENDPOINT**

## **10.1 Efficacy**

Patients must receive one full cycle of rucaparib and have PSA assessed after that cycle to be evaluable for efficacy. Patients who do not meet evaluable criteria will be replaced.

PSA levels will be monitored monthly while on treatment for comparison to baseline levels with the objective of assessing the proportion of patients with a 50% reduction in PSA levels (PSA50).

PSA progression-free survival (PSA-PFS) is defined as the time from study enrollment until the time of PSA progression as defined by PCWG3 criteria or death.

Patients who start another anti-cancer treatment prior to PSA progression or who complete one year of follow-up without PSA progression will have their data censored at that time point.

Overall survival is defined as the time from study enrollment until death. Survival will be monitored while on study and every 90 days for 2 years after study discontinuation.

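### Section 10.1 censors PSA-PFS at one year of follow-up without saying when the year starts, and the cap conflicts with the PSA testing scheduled in Sections 4.4, 8 and 9.5

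*Combined protocol and SAP*

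**What the plan says.** Section 10.1 defines the primary endpoint from enrolment: PSA-PFS "is defined as the time from study enrollment until the time of PSA progression" or death. It censors men who start another anti-cancer treatment, and also those "who complete one year of follow-up without PSA progression will have their data censored at that time point". No section gives the start of that year.

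Other sections describe a longer PSA record:

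- Section 4.4 has treatment running to PSA progression, "with 2 years of follow up after study treatment". It adds: "We anticipate a total of 2-3 years until completion of the clinical trial".
- Section 8, note 16, sets visits every 90 days "for 2 years following End of Treatment as per standard of care". Note 8 states: "If treatment is discontinued prior to PSA progression, PSA testing will continue throughout follow-up".
- Section 9.5 repeats this: "PSA testing will continue throughout follow-up until PSA progression or start of another treatment".
- Section 10.1 itself says "PSA levels will be monitored monthly while on treatment for comparison to baseline levels", and treatment has no fixed maximum length.

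Section 11.1 sets a null median of 3 months against 12, exponential, with 15 patients. Section 11.2 plans Kaplan-Meier estimates of PSA-PFS with confidence intervals.

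**The concern.** Two start dates have support in the text. End of Treatment fits the way the documents mostly use the word follow-up. Enrolment is the time origin of PSA-PFS, given in the same section as the cap. Two analysts could therefore censor the same man at different dates and obtain different primary datasets.

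Naming the start does not remove the conflict. From End of Treatment, the second of the two scheduled years does not count. From enrolment, every PSA after month 12 is left out of PSA-PFS, including monthly values in men still taking rucaparib. The hypothesis is stated as a median, so what is at stake is whether the trial can report one, with an upper limit.

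**Working it through.** **Inputs.** From Section 11.1: n = 15, exponential, median 3 months (null) or 12 months (alternative), one-sided alpha 0.05, stated power 90%. From Section 4.4: 12-month enrolment (taken as uniform) and a total of 2-3 years, so closes at 24 and 36 months after first enrolment. The documents give no rate of stopping treatment without progression. I assume 10%, 30% and 50% per year, with no other therapy started and progression times unaffected by stopping.

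**The plan's 90%.** No test is named. A normal-approximation test of the 3-month progression-free proportion (0.50 against 0.5^(3/12) = 0.841) gives 91.3%. A Wald test on the log hazard with 4.18 expected events (12-month accrual, no added follow-up) gives 88.3%. The stated figure is thus roughly reproduced, and neither calculation depends on data after month 12.

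**Year from enrolment (exact).** Expected events are 15 × (1 − 2^(−12/12)) = 7.5. With everyone followed to month 12, the Kaplan-Meier curve reaches 0.5 only at the 8th event (7/15 = 0.467), so the chance that the median is not reached is P(Bin(15, p) ≤ 7) with p = 1 − 2^(−12/m):

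| True median m (months) | p | Median not reached |
|---|---|---|
| 7.4 | 0.675 | 8% |
| 9.8 | 0.572 | 28% |
| 12 | 0.500 | 50% |
| 15 | 0.426 | 72% |

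The values 7.4 and 9.8 are the olaparib medians cited in Section 11.1.

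**Without the cap (simulation, true median 12, no early stopping).** The upper 95% limit is log-log and counts as available only where the band itself crosses 0.5.

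| | Events | Median reached | Upper limit available |
|---|---|---|---|
| Cap at 12 months from enrolment | 7.5 | 50% | 6% |
| No cap, 24-month close | 9.6 | 92% | 32% |
| No cap, 36-month close | 12.3 | 99.8% | 87% |

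**Year from End of Treatment (simulation).** Of about eight 90-day visits (days 90 to 720), the four after day 365 (days 450, 540, 630 and 720) stop counting, and only for early stoppers who are still progression-free. Results for 10%, 30% and 50% per year stopping:

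| | 24-month close | 36-month close |
|---|---|---|
| Patients censored by the clause | 0.31, 0.97, 1.72 | 0.69, 2.00, 3.24 |
| Events with the clause | 9.52, 9.38, 9.21 | 11.99, 11.37, 10.74 |
| Events with the full two years | 9.58 | 12.26, 12.19, 12.11 |
| Events lost | 0.7%, 2.1%, 3.8% | 2.2%, 6.7%, 11.3% |
| Median reached with the clause | 92%, 91%, 89% | 99.7%, 99.4%, 98.6% |

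The upper limit suffers more. At 36 months it is available in 82%, 71% and 58% of trials with the clause, against 87%, 86% and 84% with the full two years.

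**Test and lower limit.** On either reading the clause censors nobody before month 12. Whether the lower limit lies above 3 months depends only on data up to month 3, so it cannot change. In simulation the two-sided 95% lower limit exceeds 3 months in 56% of trials with the enrolment cap and in 56% without it. The level depends on the interval chosen; the equality does not. One-sample log-rank power against 3 months is 0.997 with the enrolment cap and 0.999 without it.

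The simulations use exact event times and do not model the 12-week window in Appendix B.

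**The case against.** The strongest reply is that the documents nearly settle the start date. Wherever a follow-up period is scheduled, it comes after treatment, and the calendar gives it a column separate from the cycles and End of Treatment. A man still taking rucaparib has not entered it, so he would not naturally complete a year of it. This stands: End of Treatment is the likelier reading, and on it the loss is small. The 11% figure also needs 50% per year to stop without progressing or starting anything else.

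The 50% figure arises because the assumed true median sits exactly on the cap; at 7.4 months it is 8%. That is right, although Section 11.1 hypothesises a median longer than in those earlier trials.

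The later PSA values are excluded only from PSA-PFS and still serve other purposes. A fixed horizon can also be legitimate, particularly off treatment, where visits are 90 days apart. Both points are fair, but the plan gives no reason for a one-year horizon alongside two years of PSA testing.

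A reader might infer that the cap costs the trial its power, or that the protocol plainly censors men on treatment at 12 months. The documents support neither. The null is 3 months, and the clause removes nothing before month 12. The enrolment reading is possible but is not stated.

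**Conclusion.** The point holds as an undefined start date together with a conflict between the censoring rule and the PSA schedule. On the likelier reading, from End of Treatment, about 1-4% of events are lost at a 24-month close and 2-11% at 36 months, under the assumed stopping rates. On the less likely reading, from enrolment, 7.5 events remain and the median is not reached in half of trials under the plan's own alternative. Without the cap that figure is about 8% or 0.2%.

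The consequence is confined to the Kaplan-Meier median and its upper limit. This should be corrected before analysis, but it does not threaten the hypothesis test. All sizes rest on exponential times, uniform 12-month accrual and, except where other medians are shown, a true median of 12 months.

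**What to change.** Delete the one-year clause and keep censoring at new treatment. Suggested text:

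> Patients who start another anti-cancer treatment before PSA progression or death will be censored at their last PSA assessment before that treatment, whatever happens later. All other patients without PSA progression or death by the data cut-off will be censored at their last PSA assessment on or before the cut-off.

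State the cut-off within the planned 2-3 years, for example 24 or 36 months after first enrolment. If a cap is kept, state that it runs from End of Treatment and reconcile it with the two-year PSA follow-up in Sections 4.4, 8 and 9.5.

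The cost is a short edit to Section 10.1 and one stated date; no test is added. A 24-month cut-off reports no later than a one-year cap from enrolment (12 + 12 months), but leaves the upper limit unavailable in about 68% of trials. A 36-month cut-off lowers that to about 13% and reports a year later. Off-treatment progressions are dated from 90-day visits, so on average about 45 days late (90/2) rather than 14 (28/2). The new-treatment censoring date also moves from the start of that treatment to the last PSA before it.

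How progression is dated, and the different time origin in Appendix B (start of therapy) and Section 10.1 (enrolment), are separate points.

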#### 6.2.3 Accountability and Compliance

Rucaparib tablets will be dispensed to the patient in sufficient quantity to last until Day 1 of the next treatment cycle. Patients will keep all unused tablets and containers (empty, partially used, and/or unopened) for accountability at the next visit.

Patients should take rucaparib doses as close to 12 hours apart as possible, preferably at the same times every day. If a patient misses a dose (i.e., does not take it within 4 hours of the scheduled time), the patient should skip the missed dose and resume taking rucaparib with the next scheduled dose. Missed or vomited doses should not be made up.

Patients will be instructed to record daily doses taken or not taken in a patient diary. Treatment with rucaparib is continuous and each cycle will comprise 28 days.

All study drugs will be stored at the Huntsman Cancer Institute Investigational Pharmacy in accordance with Good Clinical Practice (GCP) and GMP requirements and the instructions given by the clinical supplies department of the sponsor, and will be inaccessible to unauthorized personnel. The investigator, or a responsible party designated by the investigator, must maintain a careful record of the inventory and disposition of the agent.

An adequate record of receipt, distribution, and return of all study drugs must be kept in the form of a Drug Accountability Form. Subject compliance with the treatment and protocol includes willingness to comply with all aspects of the protocol, and to have blood collected for all safety evaluations. At the discretion of the principal investigator, a subject may be discontinued from the trial for non-compliance with follow-up visits or study drug.

Instructions on medication resupply and destruction will be made available to affected parties as applicable.

At the conclusion of the study, and, as appropriate during the course of the study, the Investigator will return all used and unused study drug, packaging, drug labels, and a copy of the completed drug accountability ledger to Clovis.

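### Section 10.1 censors PSA-PFS at the start of other treatment instead of at the last PSA, so men already off rucaparib can be credited with up to 104 days in which no PSA was taken

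*Combined protocol and SAP*

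**What the plan says.** - **Endpoint (Section 10.1).** PSA-PFS "is defined as the time from study enrollment until the time of PSA progression as defined by PCWG3", or death.
- **Censoring (Section 10.1).** One clause covers two groups: men who begin other anti-cancer therapy before PSA progression, and men who reach one year of follow-up "without PSA progression will have their data censored at that time point". The censoring date is the date of that occurrence. Neither Section 11 nor any other section moves it back to the last PSA.
- **PSA on treatment.** Section 10.1: "PSA levels will be monitored monthly while on treatment". Section 6.2.3: "each cycle will comprise 28 days". The Study Calendar allows ± 3 days and adds a PSA at the end-of-treatment visit.
- **PSA off treatment.** For men who stop before PSA progression, Study Calendar note 8 and Section 9.5 say that "PSA testing will continue throughout follow-up until PSA progression or start of another treatment". Note 16: "Follow-up should occur every 90 days", with a window of ± 14 days. No PSA is required at the switch itself.
- **Conflicting wording.** The Study Summary and Section 1.1 describe PSA as monthly, in Section 1.1 up to progression, without separating time on and off treatment.
- **Analysis.** Section 11.1 sets a null median of 3 months against 12 months, with 15 patients, one-sided alpha 0.05 and 90% power. Section 11.2 names Kaplan-Meier methods. No test of the 3-month null is named.

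**The concern.** PSA progression can be detected only at a draw. A man who has stopped rucaparib and starts other treatment between two follow-up visits has an unknown PSA status from his last draw to the switch. Section 10.1 nevertheless counts that interval as progression-free. He stays in the Kaplan-Meier risk set and adds to total time at risk while PSA progression could not have been recorded for him. The trial has a single arm and tests against a fixed 3-month median, so no comparator carries the same error.

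**Working it through.** **1. The plan's own figure.** Since no test is named, several were tried. Under the alternative, S(3 months) = 2^(−3/12) = 0.841, against 0.50 under the null.

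- Normal approximation, N = 15: [(0.841 − 0.50) − 1.645 × √(0.25/15)] / √(0.841 × 0.159/15) ≈ 1.36, so power is 91.3%.
- Arcsine version: 89.6%.
- Exponential chi-square test: 99.9% with 15 events; about 97–98% with the 7–8 events expected by 12 months (15 × 0.5 = 7.5).

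The stated 90% therefore matches a test of S(3 months). It assumes continuous observation and is not disputed here.

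**2. Longest interval without a PSA** (days / 30.4375).

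| Situation | Days | Months |
|---|---|---|
| On treatment, 28 + 3 | 31 | 1.02 |
| On treatment, windows anchored, 28 + 3 + 3 | 34 | 1.12 |
| Off treatment, nominal | 90 | 2.96 |
| Off treatment, visit to visit, 90 + 14 | 104 | 3.42 |
| Off treatment, windows anchored to end of treatment: day 76 (90 − 14) to day 194 (180 + 14) | 118 | 3.88 |

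The 104-day figure takes the window as applying to the interval between visits.

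**3. Direction.** At an event time with d events and n at risk, the Kaplan-Meier factor is 1 − d/n. Suppose c of those n men are past their last PSA and will be censored at a later switch. Last-PSA censoring gives 1 − d/(n − c), which is never larger. So the curve under Section 10.1 is never below the last-PSA curve, and total time at risk is never shorter.

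**4. Size, by simulation.** There were 15 men, 3,000 replicates per scenario, PSA every 28 days on treatment and every 90 ± 14 days off it, and a 12-month cap. Assumptions, because the documents give no rates: 0, 3% or 8% of men per month stop without progression, and new therapy starts a mean of 1.0 or 3.3 months later. The comparison arm censors every man at his last PSA. The 12-week and confirmation rules of Appendix B were not modelled.

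| Quantity | As written | Last PSA |
|---|---|---|
| True median 3: exponential test rejects | 6.7–11.4% | 5.3–6.9% |
| True median 3: Kaplan-Meier log-log lower limit above 3 months | 3.1–5.7% | 3.1–5.0% |
| True median 3: typical Kaplan-Meier median (months) | 3.7 | 3.7 |
| True median 12: Kaplan-Meier-based power | 82–88% | 80–85% |

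Monte Carlo standard error near 5% is √(0.05 × 0.95/3000) = 0.4 points. The mean credited gap among censored men was 0.3–1.1 months with some early stopping and 0.04 months with none. The latter is just 365.25 − 364 = 1.25 days at the one-year cap.

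**5. The one-year group.** Thirteen cycles are 13 × 28 = 364 days, so a man on schedule has a PSA within about a day of one year. Testing also continues past one year, each cycle on treatment and at follow-up visits off it. A later PSA without progression shows that censoring at one year was right.

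**The case against.** **The monthly wording may govern.** If the Study Summary and Section 1.1 prevail, the gap is about one month even off treatment. But Section 10.1 confines monthly PSA to time on treatment, and Section 9.5 with the Study Calendar sets the follow-up visits. The conflict is real and has to be settled; neither wording changes the censoring date.

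**The group may be small and the gap short.** This stands. The 3.4 months is a maximum for men who stopped rucaparib before progression and then switched. A PSA may also be drawn when the switch is decided, although none is required.

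**The decision hardly changes.** This stands for a Kaplan-Meier decision. The larger inflation needs a time-at-risk test that the plan does not name, though it does not exclude one either.

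**Stronger readings that a reader might infer.**
- *That the date is wrong for every censored man.* The one-year group contradicts this: most have a PSA close to, or after, that date. What starts the year is also unstated, but that is a separate matter.
- *That S(3 months) is seriously inflated by men who stop very early.* Appendix B does not count PSA rises in the first 12 weeks as progression, so almost no PSA event can fall before month 3.
- *That the reported median would change.* With a true median of 12 months and some early stopping, the typical simulated median was not reached as written and 12.0 months with last-PSA censoring. That contrast is fragile, because the true median there coincides with the 12-month cap.

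**Conclusion.** The point holds for men who stop rucaparib before PSA progression and later start other treatment. Up to 104 days (3.4 months) without a PSA can be credited to such a man; for a man still on treatment it is about one month. Compared with last-PSA censoring, the error goes one way, in favour of rucaparib. Its likely size is modest: small for a Kaplan-Meier decision, with no change in the typical median when the true median is 3 months, and larger for a time-at-risk exponential test. These sizes rest on assumed stopping and switching rates, and on the 90-day schedule governing off-treatment PSA. The documents do not support a claim that the trial's conclusion would be reversed. The error is nevertheless in the primary endpoint and easily avoided, so it should be corrected before analysis.

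**What to change.** Replace the censoring sentence in Section 10.1 and keep the one-year cap. Suggested text:

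*A patient who begins other anti-cancer therapy before PSA progression is censored at the last PSA assessment on or before the date that therapy starts. A patient who reaches one year of follow-up free of PSA progression is censored at one year if a PSA taken on or after that date shows no progression, and otherwise at the last PSA before it.*

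Also reconcile the monthly PSA wording in the Study Summary and Section 1.1 with the 90-day follow-up schedule in Section 9.5 and Study Calendar note 16.

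Cost: two sentences in Section 10.1 and a consistency edit. The censoring change uses PSA dates already collected. The stated 90% power does not change. The downside is that reported PSA-PFS becomes slightly less favourable.

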## **10.2 Safety**

Routine safety and tolerability will be evaluated from the results of reported signs and symptoms, scheduled physical examinations, vital sign measurements, and clinical laboratory test results. More frequent safety evaluations may be performed if clinically indicated or at the discretion of the investigator.

### **10.2.1 Physical Examination**

Complete and symptom-directed physical examinations will be performed by a licensed physician or appropriately delegated personnel as noted in the calendar (Section 8).

